12.1 General statistical consideration

For continuous variables, the Kolmogorov-Smirnov test will be applied to evaluate the distribution. Variables with normal distribution will be presented as means and standard deviation (SD), and intergroup comparisons will be performed using the 2-tailed, student's t test. Variables with non-normal distribution will be presented as medians and interquartile ranges (IQR), and intergroup comparisons will be performed using the Mann-Whitney U test. Categorical variables will be summarized with frequencies and percentages and compared using chi-square test or Fisher exact test, as appropriate. All statistical analysis will be conducted with the use of the statistical package SPSS, version 19.0 (SPSS Inc). A two-sided P value of <0.05 will be considered as significantly different.

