6.7 Delivery visit

When the participant is preparing to deliver, the investigator will collect the delivery information and infant information according to the form designed for this visit. The delivery information mainly includes the delivery mode and pregnancy complications. The neonate information mainly includes gender, birth weight and length, birth

defects, admission to newborn intense care unit within 1 month and stillbirth.

7. Physical examination

A physical examination will be conducted on all participants by the corresponding investigator. The parameters include height, weight and they will be recorded to the nearest 0.1 cm, 0.1 kg. Height and weight will be measured without shoes, and patients will be dressed in light clothing.

8. Transvaginal ultrasound scan

An ultrasound scan with a transvaginal probe will be carried out. Uterine dimension, endometrial thickness and type, bilateral ovarian dimension, and follicle number will be measured through the ultrasound scan. The uterine size will be determined at the widest diameter. The investigator will determine endometrial types. Endometrial thickness is the largest anterior-posterior measurement of the endometrium in the sagittal plane. Ovarian dimension is measured by analysis of the largest plane of the ovary in two dimensions. In addition, antral follicle count (AFC) will be recorded.

9. Laboratory tests

Hormone and pregnancy tests will be performed at the local laboratories. In addition, blood work will be performed on screening visit, Gn initiation visit, hCG trigger day, and 2 weeks after ET. The blood sample (5 ml) will be collected with an anticoagulant tube and stored at -80°C for further analysis.

10. Outcome measures

The live birth rate is the primary outcome. The secondary outcomes will include counts and rates of oocytes/embryos (oocytes retrieved, 2 pro-nuclei zygotes, cleavage zygotes, available embryos, high-quality embryos), pregnancy outcomes (rates of biochemical pregnancy, implantation, clinical pregnancy and miscarriage),

incidences of maternal, fetal and neonatal complications, neonate information (newborn birthweight and length, congenital malformation) (14).

Live birth is defined as delivery of any viable infants after 28 weeks of gestation.

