The number of oocytes retrieved will be defined as the total number of oocytes retrieved through ultrasound-guided transvaginal aspiration. The rate of oocytes retrieved will be defined as the number of retrieved oocytes divided by the number of follicles with a diameter ≥ 10 mm on the HCG injection day. Matured oocytes will be defined as those with pronuclei or polar bodies observed on Day 1 after oocyte retrieval in IVF patients, or as the number of MII oocytes on the day of oocyte retrieval in ICSI patients. Cleavage oocytes will be defined as the number of fertilized oocytes that undergo cleavage on Day 2 after oocyte retrieval. The rate of cleavage will be defined as the number of cleaved embryos divided by the number of fertilized oocytes (2PN + 1PN + multiple PN). Available embryos will be defined as the sum of the number of embryos transferred and the number of embryos frozen. The rate of available embryos will be defined as the number of available embryos divided by the number of cleaved oocytes. High-quality embryo will be defined according to the day of embryo transfer, following the Istanbul consensus and Gardner criteria, Day 2: 4 cells, cell fragments $<10\%$ and no multi-nucleus; Day 3: 8 cells, cell fragments $<10\%$, no multi-nucleus; Day 5: stage 4 blastocyst, grade A inner cell mass, grade A trophectoderm (12,13). The rate of high-quality embryos will be defined as the number of high-quality embryos divided by the number of available embryos.

Biochemical pregnancy will be defined as positive when β -HCG >50 IU/L. Implantation rate will be defined as the number of gestational sacs per the number of embryos transferred. Clinical pregnancy will be defined as the presence of intrauterine gestation sac with fetal motion under transvaginal ultrasonography. Miscarriage rate will be calculated among patients with biochemical pregnancies and patients with clinical pregnancies.

Incidence of maternal, fetal and neonatal adverse events were assessed, including moderate or severe OHSS, gestational diabetes mellitus (GDM), gestational

hypertension, postpartum hemorrhage, preterm delivery, congenital anomalies, puerperal infection, stillbirth, neonatal jaundice, neonatal infection, neonatal death, ectopic pregnancy, and low birth weight infant. The definitions of these safety indexes were shown in **Table 6**.

Table 6. Definitions of safety outcomes

Safety outcome	Definitions

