12.3 Type of analysis

We will utilize an intent-to-treat approach to examine differences in the live birth rates for the first embryo transfer cycle in the two treatment arms in the primary analysis by the Pearson χ^2 test. Safety parameters and secondary efficacy parameters, such as pregnancy rate, miscarriage rate and other rates, will be analyzed using the Pearson χ^2 test or Fisher exact test as appropriate. Secondary efficacy parameters, including the counts and rates of oocytes/embryos, will be analyzed using the Mann-Whitney U test.

For the primary and secondary outcomes, we will also perform analysis in the per-protocol set (PPS), excluding those who have major protocol deviation(s), cancel cycle or do not complete the pre-set minimum exposure dosage of the assigned study drug (at least 80% compliance), from the ITT population. Subgroup analysis will be conducted as stratified by age (35-37, 38-39, 40-42).

Prior to unblinding, missing value in the primary outcome (live birth) and secondary outcomes (biochemical pregnancy, clinical pregnancy) in the ITT analysis will be imputed as not having an event.

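### About 15 secondary efficacy tests share one unadjusted P<0.05 rule; if ZYP does nothing, the chance of at least one false significant result is up to about 54% in the ITT set (about 32% favouring ZYP)

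*Combined protocol and SAP*

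**What the plan says.** - **Decision rule (section 12.1).** "A two-sided P value of <0.05 will be considered as significantly different". The sentence is not limited to the primary outcome.
- **Primary analysis (section 12.3).** "We will utilize an intent-to-treat approach to examine differences in the live birth rates for the first embryo transfer cycle", by the Pearson chi-square test. Live birth is the only primary outcome, and section 12.4 plans no interim analysis.
- **Secondary efficacy outcomes (section 10).** These are "counts and rates of oocytes/embryos (oocytes retrieved, 2 pro-nuclei zygotes, cleavage zygotes, available embryos, high-quality embryos" and "pregnancy outcomes (rates of biochemical pregnancy, implantation, clinical pregnancy and miscarriage". Section 10 adds: "Miscarriage rate will be calculated among patients with biochemical pregnancies and patients with clinical pregnancies". Section 12.3 assigns formal tests to them: chi-square or Fisher exact for pregnancy rates, Mann-Whitney for oocyte and embryo measures.
- **Second analysis set (section 12.3).** "For the primary and secondary outcomes, we will also perform analysis in the per-protocol set (PPS". The PPS is formed by removing participants "from the ITT population".
- **Subgroups (section 12.3).** Three age bands are to be analysed. The plan does not say for which outcomes.

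No section ranks the secondary outcomes, adjusts for their number, calls them exploratory, or makes a secondary claim depend on the live-birth result.

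**The concern.** A 5% error rate belongs to one test. When one threshold serves a long list of outcomes and nothing in the plan separates confirmatory from descriptive results, the chance of a significant finding somewhere on the list is far above 5%, even if the drug does nothing.

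What is at stake is the standing of secondary claims. If live birth shows no difference, section 12.1 still allows clinical pregnancy, or a single embryo measure, to be called significantly different on the same terms as the primary outcome. A reader of the report could not tell from the plan how much weight such a result deserves.

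**Working it through.** **1. The plan's own figure.** Section 12.2 sizes the trial on one test: 0.42 against 0.33, two-sided 0.05, power 80%. With pooled variance under the null (mean rate 0.375):

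n = [1.960·√(2×0.375×0.625) + 0.842·√(0.42×0.58 + 0.33×0.67)]² / 0.09² = 453.04, so 454 per group.

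Allowing for 38% loss: 454/0.62 = 732.3, so 733 per group and 1466 in total. Both figures reproduce. No alpha is shared with other outcomes, so nothing below changes them.

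**2. Number of secondary efficacy tests (section 10).**
- Oocyte and embryo measures: 5 counts and 5 rates = 10. Section 10 defines no rate for 2-pronuclei zygotes; without it, 9.
- Pregnancy measures: biochemical pregnancy, implantation, clinical pregnancy, and miscarriage on two denominators = 5.
- Total: 14 to 15 in the ITT set, and 28 to 30 P values with the PPS repeat. Age subgroups and safety tests are not counted.

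**3. Independent tests, no true effect, ITT only.** A two-sided 0.05 test gives a false result favouring ZYP with probability 0.025.

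| Tests | Either direction | Favouring ZYP |
|---|---|---|
| 14 | 1 − 0.95¹⁴ = 51.2% | 1 − 0.975¹⁴ = 29.8% |
| 15 | 1 − 0.95¹⁵ = 53.7% | 1 − 0.975¹⁵ = 31.6% |

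The expected number of false results from 15 tests is 15 × 0.05 = 0.75, of which 15 × 0.025 = 0.375 favour ZYP. Independence is the upper end when the test statistics are positively correlated.

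**4. Correlated tests and the PPS repeat.** The documents give no correlations, so the values here are assumptions. The 15 test statistics were simulated as multivariate normal (200,000 draws) in two families, 10 oocyte/embryo and 5 pregnancy. The PPS was added as a second copy correlated 0.7 to 0.9 with the ITT result. For orientation, if the PPS kept 62% of the ITT population, the correlation would be about √0.62 = 0.79.

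| Correlation within / between families | ITT, either direction | ITT, favouring ZYP | ITT + PPS, either direction | ITT + PPS, favouring ZYP |
|---|---|---|---|---|
| 0 / 0 | 53.7% | 31.6% | 66.5–73.0% | 41.6–47.3% |
| 0.3 / 0.1 | 48.2% | 25.4% | 60.6–67.4% | 33.3–38.1% |
| 0.5 / 0.1 | 41.6% | 21.6% | 53.0–59.5% | 28.3–32.2% |
| 0.7 / 0.2 | 32.4% | 16.5% | 42.2–48.1% | 21.7–25.1% |

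A further run with 0.5 within the oocyte/embryo family, 0.7 within the pregnancy family and 0.2 between them fell inside these ranges.

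**The case against.** The strongest reply is that the trial's main claim is protected. There is one primary outcome, one primary test in the ITT population, a sample size built on that test alone, and no interim look. Everything else is labelled secondary, and many readers treat secondary outcomes as supportive by default. All of this stands for live birth. It does not cover the secondary claims, because the plan never says they are supportive only, and section 12.1 gives them the same threshold and the same label.

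A second reply is that independence is unrealistic. Oocytes retrieved, fertilised, cleaved, available and high-quality form a chain. Clinical pregnancy is assessed only after a positive pregnancy test, and the two miscarriage rates differ in denominator. This also stands, and it is why the correlated rows of the table deserve more weight than the 54%.

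Two stronger readings are tempting, and the documents do not support either.

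- **That a false benefit of ZYP is more likely than not.** The 54% counts results in either direction and assumes independence. For results favouring ZYP, 50% is passed only at 28 or more independent tests (1 − 0.975²⁸ = 50.8%). That would need the PPS to be independent of the population it is drawn from. Age subgroups could push the figure past 50% if they covered every secondary outcome: with three equal strata added to the overall ITT tests, simulation gives about 58% at a common correlation of 0.3 and 47% at 0.5. The plan does not say that they do.
- **That this repeats the weakness the trial was meant to cure.** The Background describes the clinical-pregnancy result of the sponsor's previous trial as a post hoc subgroup analysis without adequate power. That is not a statement about multiplicity, and the present outcomes are prespecified.

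Nor does any section say that a secondary result may take the place of live birth in the conclusion.

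**Conclusion.** The concern holds for secondary efficacy claims. A stated rule, not merely a missing detail, lets about 14 to 15 comparisons, repeated in the PPS, each be called significant at 0.05.

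If ZYP has no effect on these outcomes, the chance of at least one false significant result is:
- ITT set, independent tests: up to about 54% in either direction, and up to about 32% favouring ZYP.
- ITT set, within-family correlation 0.3 to 0.7: about 32% to 48% in either direction, and 17% to 25% favouring ZYP.
- ITT plus PPS, favouring ZYP: about 22% to 38% with those correlations, and up to about 47% if outcomes are independent.

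Even the lowest of the figures favouring ZYP is well above the 2.5% that a single two-sided test allows in that direction. The results rest on the count in section 10, on no true effect on any secondary outcome, and on assumed correlations. This deserves correction but does not threaten the primary inference.

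**What to change.** In section 12.1, limit the confirmatory P<0.05 rule to the ITT live-birth test. State in section 12.3 that all secondary efficacy, PPS and age-subgroup results will be reported as effect estimates with 95% confidence intervals, labelled exploratory and not adjusted for multiplicity. Name the outcomes to which the age subgroups apply.

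If the sponsor wants a confirmatory secondary claim, it should specify a short fixed sequence before unblinding, each step tested at 0.05 only if live birth and every earlier step succeeded. Clinical pregnancy first is one possible order; the documents do not dictate one, and the choice is the sponsor's.

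Write the restriction for efficacy only. Section 10 also lists maternal, fetal and neonatal complications and congenital malformation among the secondary outcomes. Those safety comparisons should stay outside it and be reported as planned.

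The change is to wording alone; the primary alpha and the 1466 participants are unchanged. The cost is that fewer secondary results can be called significant.

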12.2 Sample size estimation

In our previous clinical research, the live birth rate was 0.42 per embryo transfer in ZYP treated group and 0.33 per embryo transfer in placebo control group among AMA women. By assuming the same live birth rates, a sample size of 454 women in each group can provide a power of 80% at a significance level of 0.05. According to previous study, the dropout rate before ET was 15% and the cycle cancellation rate was 23% in AMA women. For this trial, a total rate of 38% (dropout and cancellation) is considered in the sample size calculation. Therefore, a total of 1466 participants

will be recruited in this study, 733 participants in each group.

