5.1 General design

It will be a multicenter, prospective, randomized (1:1 treatment ratio) clinical trial comparing the live birth rates in AMA women assigned to these treatment arms after a fresh ET in 1466 infertile patients undergoing IVF or ICSI. Patients will be randomized into either of two groups, receiving ZYP or the placebo during IVF/ICSI. All of the participants will receive standardized controlled ovarian hyperstimulation (COH) protocols, i.e., GnRH agonist (GnRH-a) long protocol or GnRH antagonist (GnRH-ant) protocol), as appropriate, and then undergo embryo transfer (ET).

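### The 80% power in section 12.2 is for women who reach transfer; with the plan's own 38% loss, equal in both arms and scored as no live birth, the intent-to-treat primary test has about 72%

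*Combined protocol and SAP*

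**What the plan says.** Section 12.2 bases the sample size on earlier work in which "the live birth rate was 0.42 per embryo transfer in ZYP treated group and 0.33 per embryo transfer in placebo control group". From these rates it concludes that "a sample size of 454 women in each group can provide a power of 80% at a significance level of 0.05". It then adds a 15% dropout rate before transfer to a 23% cancellation rate, so that "a total rate of 38% (dropout and cancellation) is considered in the sample size calculation", and arrives at 733 per group, 1466 in total.

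Section 12.3 describes the primary analysis: "We will utilize an intent-to-treat approach to examine differences in the live birth rates for the first embryo transfer cycle", by the Pearson chi-square test. The per-protocol set is formed by "excluding those who have major protocol deviation(s), cancel cycle or do not complete the pre-set minimum exposure dosage of the assigned study drug". The same sentence makes clear that these women are taken out of the intent-to-treat set, and so belong to it beforehand. Missing live birth "in the ITT analysis will be imputed as not having an event".

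Section 5.1 describes the trial as "comparing the live birth rates in AMA women assigned to these treatment arms after a fresh ET". No section says outright how a randomised woman who has no transfer is scored for the primary outcome.

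**The concern.** Dividing by 0.62 is right if the 38% leave the analysis and the remaining women are compared at 42% and 33%. It is not enough if they stay in the denominator without a live birth. Recruiting more women then replaces the lost transfers, but both rates, and the difference between them, shrink by the factor 0.62. Section 12.2 does not make that conversion.

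Two readings of the primary analysis have to be kept apart.

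1. **Per woman randomised, no fresh transfer scored as no live birth.** The intent-to-treat label supports this. So does the per-protocol definition: cancelled cycles can be removed from the ITT population only if they are in it. The imputation rule and the fresh-transfer wording in 5.1 point the same way.
2. **Per transfer.** The reference in 12.3 to the first embryo transfer cycle, and the wording of 5.1, could be read this way, and it matches 12.2. But women with a transfer are a subset defined after randomisation, so this is not intent-to-treat. It would also leave no cancelled cycles for the per-protocol set to remove.

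On the first reading, the plan's only power figure does not describe its primary test, and a null result would be judged against a power the test does not have. While the denominator is unstated, the choice between per-woman and per-transfer results also remains open.

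**Working it through.** **Inputs.** Rates 0.42 and 0.33 per transfer; 15% dropout and 23% cancellation, 38% in total; 733 per group (all 12.2). Two-sided 0.05 (12.1). Pearson chi-square test (12.3). Allocation 1:1 (5.1).

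**Formulas.** Pooled two-proportion comparison, with d = p1 − p2 and p̄ = (p1 + p2)/2:

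- n per group = [1.960·√(2p̄(1−p̄)) + 0.842·√(p1(1−p1) + p2(1−p2))]² / d²
- power = Φ{ [d·√n − 1.960·√(2p̄(1−p̄))] / √(p1(1−p1) + p2(1−p2)) }

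**Step 1: reproduce the plan.** With 0.42 and 0.33, p̄ = 0.375 and n = (1.3419 + 0.5737)² / 0.0081 = 453.04, so 454. Power at 454 is 0.801. Inflation: 454/0.62 = 732.3, so 733. Both figures reproduce. Conversely, 733 × 0.62 = 454.5, so the 454 are the women expected to reach transfer.

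**Step 2: convert to rates per woman randomised.** With 38% of each arm scored as no live birth:

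- ZYP: 0.62 × 0.42 = 0.2604
- placebo: 0.62 × 0.33 = 0.2046
- difference: 0.0558, against 0.09 per transfer

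**Step 3: power of the ITT test at 733 per group.** p̄ = 0.2325; d·√733 = 1.5107; 1.960·√0.35689 = 1.1709; √0.35533 = 0.5961. Power = Φ[(1.5107 − 1.1709)/0.5961] = Φ(0.570) = 0.716. Exact enumeration of the uncorrected chi-square test gives 0.717. A simulation of 1,000,000 trials, each woman transferred with probability 0.62, gives 0.801 for the per-transfer test and 0.717 for the ITT test on the same trials.

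**Step 4: sensitivity, all at 733 per group.**

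| Assumption | ZYP v placebo | Power |
|---|---|---|
| 38% equal loss (the plan's figure) | 26.04% v 20.46% | 71.6% |
| Losses multiplied, 1 − 0.85 × 0.77 = 34.55% (not the plan's figure) | 27.49% v 21.60% | 74.6% |
| Equal retention of 72.2% (about 529 of 733) | 30.32% v 23.83% | 80.0% |
| Retention 60% ZYP, 62% placebo | 25.20% v 20.46% | 58.0% |
| Retention 63.5% ZYP, 62% placebo | 26.67% v 20.46% | 80.0% |
| Retention 64% ZYP, 62% placebo | 26.88% v 20.46% | 82.5% |

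For information only, 80% power at 26.04% v 20.46% would need 898.5, so 899 per group.

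**The case against.** The strongest reply is that the scoring rule is inferred. The imputation rule covers missing values, and a cancelled cycle with known follow-up is not plainly missing. If the analysis is per transfer, 12.2 is internally correct at 80.1%. This stands to the extent that 72% must always carry its condition. It does not rescue the plan as written, because a per-transfer denominator is not intent-to-treat and contradicts the per-protocol definition. On either reading 12.2 and 12.3 need reconciling.

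Second, a later frozen transfer might count. If 25%, 50% or 100% of the cancelled 23% had a counted transfer at the same per-transfer rates, power would be 76.5%, 81.0% or 88.2%. Frozen embryos do appear in section 10 and Table 7. But 5.1 specifies fresh transfer, 6.1 schedules a single transfer visit, and nothing provides for counting a frozen transfer in the primary outcome. So wide a range under an unstated rule is itself a reason to state the rule.

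Third, 72% depends on equal loss. Study drug starts before stimulation, so an effect on reaching transfer is possible, and the table shows that 2 points of difference in retention moves power to 58.0% or 82.5%. This stands as a condition. Equal loss is also what 12.2 assumes.

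Fourth, section 4.3 does not say whether dropouts are followed for live birth, and the effect of counting such births can go either way. If they add equally to both arms, power falls to 66–71%, assuming that 5–15% of randomised women are such dropouts with a 10–33% live birth rate. If instead 25%, 50% or 100% of the 15% who drop out had a counted transfer at 0.42 v 0.33, power would be 74.9%, 77.9% or 83.4%. None of these inputs is in the documents, so neither range replaces the main figure.

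**Conclusion.** The concern holds. The arithmetic in 12.2 is correct, but its 80% belongs to about 454 women per group who reach transfer. On the best-supported reading of 12.3, the primary test compares 26.04% with 20.46% in 733 women per group and has 71.6% power, so the chance of missing the assumed effect is about 28% instead of 20%.

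This rests on three assumptions: the plan's per-transfer rates are right; the 38% loss is the same in both arms; and a woman without a fresh transfer counts as having no live birth. The first two are the plan's own. The third is inferred from 5.1 and 12.3, so confidence is medium. Type I error and the validity of the test are not affected. This is a point that should be fixed.

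**What to change.** 1. In 12.3, state the primary denominator and scoring: live birth from the fresh transfer of the randomised cycle, per woman randomised, with no transfer counted as no live birth. This agrees with 5.1 and the intent-to-treat wording. If the sponsor means a per-transfer analysis, it should not be called intent-to-treat, and the per-protocol definition must be changed to match.
2. In 12.2, keep the calculation but label 454 per group and 80% as applying to women who reach transfer. Beside it, give the assumed rates per woman randomised (about 26.0% and 20.5%) and the power of the ITT primary test at 733 per group: about 72%, or about 75% if the losses multiply. Write out the equal-loss assumption.

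The change is text in two sections. Because step 1 fixes the estimand, it should be made before unblinding. It needs no added patients and no new analysis; the only cost is a less favourable stated power.
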